10.3.1.	Safety Analyses	56
10.3.1.1.	Clinical Evaluation of Safety	56
10.3.1.2.	Statistical Evaluation of Safety	56
10.3.2.	Pharmacokinetic Analyses	57
10.3.2.1.	Pharmacokinetic Parameter Estimation	57
10.3.2.2.	Pharmacokinetic Statistical Inference	57
10.3.3.	Pharmacodynamic Analyses	58
10.3.3.1.	Pharmacodynamic Parameter Estimation	58
10.3.3.2.	Pharmacodynamic Statistical Inference	58
10.3.4.	Interim Analyses	59
11.	References	60

List of Tables

Table		Page
Table ITSL.1.	Objectives and Endpoints	24
Table ITSL.2.	Treatments Administered.....	40

List of Figures

Figure

Page

Figure ITSL.1. Illustration of study design for Protocol I8B-MC-ITSL.....26

List of Appendices

Appendix		Page
Appendix 1.	Abbreviations and Definitions	61
Appendix 2.	Clinical Laboratory Tests.....	65
Appendix 3.	Study Governance, Regulatory and Ethical Considerations	66
Appendix 4.	Hepatic Monitoring Tests for Treatment-Emergent Abnormality	69
Appendix 5.	Blood Sampling Summary	70
Appendix 6.	Oral Glucose Tolerance Test.....	71
Appendix 7.	Protocol Amendment I8B-MC-ITSL(a) Summary A Mixed Meal Tolerance Test Study to Evaluate the Pharmacokinetics and Pharmacodynamics of LY900014 Compared to Humalog Following a Single Dose in Adults with Type 1 Diabetes	72

1. Protocol Synopsis

Title of Study:

A Mixed Meal Tolerance Test Study to Evaluate the Pharmacokinetics and Pharmacodynamics of LY900014 Compared to Humalog Following a Single Dose in Adults with Type 1 Diabetes

Rationale:

This study in patients with type 1 diabetes mellitus (T1DM) aims to compare the pharmacokinetic (PK) profiles of insulin lispro after administration of LY900014 and Humalog and their impact on postprandial blood glucose during a standardised mixed meal tolerance test (MMTT). Furthermore, this study plans to characterise the PK and pharmacodynamics (PD) of insulin aspart analogues NovoRapid® and FIASP® in patients with T1DM under identical study conditions. A non-diabetic healthy subject cohort is included in the study to characterise “normal” insulin secretory and glucose response during an identical standardised meal. Healthy subjects will not receive any of the study drugs.

Evaluation of these meal-time insulins in the context of a standardised test meal cannot be used to infer clinical efficacy with the same rigour as a glycated haemoglobin assessment following long-term treatment. However, assessment of these analogue insulin formulations under identical conditions provides a unique opportunity to obtain comparative information on the PK and PD in a setting appropriate for evaluation of meal-time insulin.

Objective(s)/Endpoints:

Objectives	Endpoints

Primary
 
1. To evaluate the differences in PK between LY900014 and Humalog following a single dose in patients with T1DM
	
1. Early 50% t_{max} and AUC(0-30min)

Secondary
 
1. To characterise the PK profiles of LY900014, Humalog, NovoRapid and FIASP following a single dose in patients with T1DM
 
2. To evaluate the differences in PD between LY900014 and Humalog following a single dose in patients with T1DM
 
3. To characterise the PD response to LY900014, Humalog, NovoRapid and FIASP, as assessed by the MMTT, in patients with T1DM
	
1. Early 50% t_{max}
 
2. $\Delta AUC(0-1h)$, $\Delta AUC(0-5h)$
 
3. $\Delta AUC(0-1h)$, $\Delta AUC(0-5h)$

Abbreviations: AUC(0-30min) = area under the concentration versus time curve from time 0 to 30 minutes; ΔAUC = area under the baseline subtracted glucose concentration versus time curve; $\Delta AUC(0-1h)$ = ΔAUC from time 0 to 1 hour postmeal; $\Delta AUC(0-5h)$ = ΔAUC from time 0 to 5 hours postmeal; early 50% t_{max} = time to early half-maximal drug concentration; MMTT = mixed meal tolerance test; PD = pharmacodynamics; PK = pharmacokinetics; T1DM = type 1 diabetes mellitus.

Summary of Study Design:

Study I8B-MC-ITSL is a clinical pharmacology, patient- and investigator-blind, randomised, 4-treatment, 4-period crossover study in patients with T1DM. The study also involves healthy subjects who will undergo a single MMTT but will not receive any study drug.

Treatment Arms and Planned Duration for an Individual Patient with T1DM:

Patients will be screened over a 14-day period prior to start of a 7- to 14-day lead-in (insulin transition) period. Patients will then participate in a dose-finding assessment (1 to 7 days prior to MMTT in Period 1) and subsequently randomised to 1 of 4 treatment sequences according to the actual randomisation table provided to the clinical research unit (CRU). In each study period, patients will undergo a MMTT. Each patient will receive a single individualised subcutaneous (SC) injection of LY900014, Humalog, FIASP or NovoRapid immediately before the standardised test meal. All treatment procedures will be inpatient stays of approximately 2 days per period and require a maximum of 6 weeks to complete 4 periods. Each study dosing will be separated by a minimum of 21 hours and may occur on consecutive days; however, patient inclusion is subject to required screening criteria. The follow-up or early discontinuation visit should occur at least 14 days after the last dose of the study drug.

Treatment Arms and Planned Duration for an Individual Healthy Subject:

Subjects will be screened over a 28-day period prior to the MMTT. Subjects will be admitted to the CRU the evening before the MMTT. Each subject will receive a standardised test meal on Day 1. Subjects will remain inpatient in the CRU for 2 days.

Treatment (applicable to patients):

For a given patient, the single individualised dose will be the same for all the treatments.

LY900014: Single individualised SC dose per assessment period

Humalog: Single individualised SC dose per assessment period

FIASP: Single individualised SC dose per assessment period

NovoRapid: Single individualised SC dose per assessment period

Number of Patients and Subjects:

Up to 74 patients with T1DM may be enrolled so that approximately 64 patients complete the study. Replacement patients will adopt all 4 assigned crossover treatments of the original patient's randomisation schedule.

For the healthy subject cohort, sufficient subjects will be enrolled to have 12 healthy subjects complete the study.

Statistical Analysis:

Primary statistical analyses of PK and PD parameters will be conducted on the set of patients who complete all treatment periods with identical prandial insulin doses for the MMTTs during the study. Supportive analyses may be done on the key parameters for the patients who complete at least 2 treatment periods. Safety analyses will be conducted on the set of patients receiving at least 1 dose of the study drug to which they are randomised, regardless of whether or not they completed all protocol requirements.

Unless otherwise noted, all tests of treatment effects will be conducted at a 2-sided alpha level of 0.05, and confidence intervals (CIs) will be calculated at 95%, 2-sided. No multiplicity test adjustment will be made for secondary objectives.

Safety: All investigational product- and protocol procedure-related adverse events will be listed, and if the frequency of events allows, safety data will be summarised using descriptive methodology. Safety parameters will be listed and summarised using standard descriptive statistics.

Pharmacokinetic:

The mixed-effects model will be used for the analysis of the PK time parameters (time to early half-maximal drug concentration [early 50% t_{max}], time to late half-maximal drug concentration [late 50% t_{max}] and time to maximum observed drug concentration [t_{max}]) without log transformation. Least-squares means (LSmeans), treatment differences in LSmeans and the corresponding 95% CIs for the treatment differences will be estimated from the model. The p-value on the difference between LSmeans will be used to determine statistical significance. The treatment ratios and 95% CIs for the ratios will be calculated using Fieller's theorem.

Log-transformed area under the concentration versus time curves (AUCs), maximum observed drug concentration (C_{max}) for insulin lispro/aspart may be evaluated to estimate geometric means, ratios of geometric means and their corresponding 95% CIs using the same mixed-effect model as PK time parameters.

Pharmacodynamics:

Data will be analysed for the patients during each MMTT. The change from baseline values (the average of -30, -15 and 0 minutes) represented as the 0-hour time point following the start of the MMTT for each patient will be calculated. The area under the baseline subtracted glucose concentration versus time curve from time 0 to 1 hour post-meal ($\Delta AUC[0-1h]$), area under the baseline subtracted glucose concentration versus time curve from time 0 to 2 hours post-meal ($\Delta AUC[0-2h]$) and area under the baseline subtracted glucose concentration versus time curve from time 0 to 5 hours post-meal ($\Delta AUC[0-5h]$) will be calculated. In addition, the change from baseline maximum glucose observed during the 5 hours post-meal and change from baseline 1 hour glucose and 2 hour glucose after the start of the meal will be calculated. Other partial $\Delta AUCs$ may be calculated, as deemed appropriate.

Summary statistics will be presented by treatment. All PD parameters (including $\Delta AUCs$, glucose changes from baseline and time parameters) on the original scale will be analysed using the mixed-effects model that includes treatment, sequence and period as fixed effects and patient within sequence as a random effect. The p-value on the difference between LS means will be used to determine statistical significance and the corresponding 95% CIs for the LSmean ratios from Fieller's theorem will be presented.

2. Schedule of Activities

Study Schedule Protocol I8B-MC-ITSL for Patients with T1DM

Procedure	Screening	Lead-In	Dose-Finding Assessment	Study Period (Periods 1 to 4)		Follow-up/Early Discontinuation	Comments
				Day -1	Day 1		
Informed consent	X	7-14 days prior to dose-finding assessment	1-7 days prior to Period 1, Day 1			≥14 days after discharge	At least 1 day before screening procedures. Screening procedures should take place no later than 28 days after signing the informed consent.
Medical history and physical examination	X						
Height	X						At screening only.
Weight	X			X		X	Period 1 only.
Vital signs (supine): blood pressure and pulse rate	X				Predose and 420 minutes postdose	X	
12-lead ECG (supine)	X				Predose (Period 1)	X	Single ECGs will be collected for safety.
Clinical laboratory tests	X		X		Predose for Period 1 only	X	Fasting laboratory test. All clinical laboratory tests will be analysed at a local laboratory (see Section 9.4.2).
Alcohol breath test				X			Alcohol breath test to be done at admission for all periods.

Procedure	Screening	Lead-In	Dose-Finding Assessment	Study Period (Periods 1 to 4)		Follow-up/Early Discontinuation	Comments
	Up to 14 days prior to lead-in	7-14 days prior to dose-finding assessment	1-7 days prior to Period 1, Day 1	Day -1	Day 1	≥14 days after discharge	
Lead-in/insulin transition activities		X					Once patients have completed screening procedures, they will switch from prescribed basal insulin to site-provided insulin glargine. Patients will receive general diabetes training. A patient diary will be provided for recording dosing and other required information (Section 5.1.1.1). Lead-in period may be extended by 2 days as needed.
Patient admission to CRU				X			Admitted to CRU on the evening of Day -1 for all study periods. If the dose-finding assessment occurs from Day -2, the patient may continue to remain inpatient in the CRU until the completion of study MMTT for Period 1.

Procedure	Screening	Lead-In	Dose-Finding Assessment	Study Period (Periods 1 to 4)		Follow-up/Early Discontinuation	Comments
	Up to 14 days prior to lead-in	7-14 days prior to dose-finding assessment	1-7 days prior to Period 1, Day 1	Day -1	Day 1	≥14 days after discharge	
Dose-finding MMTT			X				Patients will undergo dose-finding assessment with Humalog and a standardised test meal. Dose-finding MMTT will occur after the insulin transition. Dose-finding assessment should occur between 1 and 7 days prior to MMTT in Period 1. To take place between 0700 hours and 1100 hours. See Section 5.1.1.2 for rescheduling.
Randomisation				X			To take place before run-in of Period 1 Day 1.
Pregnancy test	X			X		X	For female patients only. Serum pregnancy test will be performed at screening and urine pregnancy tests will be performed at the time of admission in Periods 1 to 4 and at follow-up (see Appendix 2).
Standardised dinner				X			Approximately at 1900 hours. The evening dinner will be identical for every period.

Procedure	Screening	Lead-In	Dose-Finding Assessment	Study Period (Periods 1 to 4)		Follow-up/Early Discontinuation	Comments
				Day -1	Day 1		
Medical assessment	Up to 14 days prior to lead-in	7-14 days prior to dose-finding assessment	1-7 days prior to Period 1, Day 1	X	Pre-dose and before discharge from CRU	X	Medical assessment includes medical review and targeted examination, and as appropriate review of concomitant medication, patient diary and MMTT exclusion criteria (see Section 6.2.1).
Glucose stabilisation/run-in					X		From approximately 7 hours to 30 minutes before dosing: IV infusion of glucose (dextrose solution) and/or insulin glulisine to achieve a target blood glucose level of 135±15 mg/dL (7.5±0.8 mmol/L). Blood glucose concentrations will be monitored at a minimum of 30-minute intervals (see Sections 9.6.1 and 5.1.1.3). See Section 6.2.3 for rescheduling.

Procedure	Screening	Lead-In	Dose-Finding Assessment	Study Period (Periods 1 to 4)		Follow-up/Early Discontinuation	Comments
				Day -1	Day 1		
Blood glucose sampling (MMTT)	Up to 14 days prior to lead-in	7-14 days prior to dose-finding assessment	1-7 days prior to Period 1, Day 1		-30, -15, 0 minutes pre-meal, 10, 20, 30, 40, 50, 60, 70, 80, 90, 100, 110, 120, 135, 150, 165, 180, 195, 210, 225, 240, 300 minutes post-meal	≥14 days after discharge	0-minute time point sample to be taken at the start of the meal.
Study MMTT					X		Standardised test meal will be administered at approximately 0700 hours (with allowance up to 1100 hours) and should be consumed within 15 minutes (see Section 5.1.1.3). MMTT may occur on consecutive days.
Study drug administration					X		Immediately before the start of meal according to the randomisation schedule: Study drug will be administered at approximately the same time on Day 1 of Periods 1 to 4. There will be at least 21 hours between study doses.

Procedure	Screening	Lead-In	Dose-Finding Assessment	Study Period (Periods 1 to 4)		Follow-up/Early Discontinuation	Comments
				Day -1	Day 1		
Insulin lispro/insulin aspart PK sampling	Up to 14 days prior to lead-in	7-14 days prior to dose-finding assessment	1-7 days prior to Period 1, Day 1		0 (predose), 1, 2, 3, 5, 10, 15, 20, 25, 30, 35, 40, 45, 50, 55, 60, 70, 90, 120, 150, 180, 240, 300, 360 and 420 minutes postdose	≥14 days after discharge	Sampling times are relative to the time of study drug administration in each period.
Discharge from CRU					X		Patients may be discharged after all study procedures are completed. Patients may be offered a meal following completion of all PK and PD assessments.

Abbreviations: CRU = clinical research unit; ECG = electrocardiogram; MMTT = mixed meal tolerance test; PD = pharmacodynamics; PK = pharmacokinetics.
 Note: The CRU should schedule activities as appropriate. In cases where several study procedures are scheduled at the same time, the order of priority will be as follows: PK samples including sampling for blood glucose and laboratory samples per protocol nominal times. ECGs and vital sign measurements should be scheduled before but as close as possible to the PK sampling times.

Study Schedule Protocol I8B-MC-ITSL for Healthy Subjects

Procedure	Screening	Study Period		Comments
	Days -28 to -2	Day -1	Day 1	
Informed consent	X			At least 1 day before screening procedures. Screening procedures should take place no later than 28 days after signing the informed consent.
Medical history and physical examination	X			
Height	X			At screening only.
Weight	X	X		
Vital signs (supine): blood pressure and pulse rate	X			
12-lead ECG (supine)	X			Single ECGs will be collected for safety.
Clinical laboratory tests	X			Fasting laboratory test. Laboratory tests will be analysed at a local laboratory.
Oral glucose tolerance test	X			Plasma glucose measurements before ingestion of glucose beverage and at 1 and 2 hours after the start of ingestion of glucose beverage.
Subject admission to CRU		X		Admitted to CRU on the evening of Day -1.
Pregnancy test	X	X		For female subjects only. Serum pregnancy test will be performed at screening and urine pregnancy tests will be performed at admission to the CRU (see Appendix 2).
Standardised dinner		X		Approximately at 1900 hours.
Medical assessment		X	Before discharge from CRU	Medical assessment includes medical review and targeted examination, and as appropriate review of concomitant medication and MMTT exclusion criteria (see Section 6.2.2).
Blood glucose sampling (MMTT)			-30, -15, 0 minutes pre-meal, 10, 20, 30, 40, 50, 60, 70, 80, 90, 100, 110, 120, 135, 150, 165, 180, 195, 210, 225, 240, 300 minutes post-meal	0-minute time point sample to be taken at the start of the meal.

Procedure	Screening	Study Period		Comments
	Days -28 to -2	Day -1	Day 1	
MMTT			X	Standardised test meal will be administered at approximately 0700 hours (with allowance up to 1100 hours) and should be consumed within 15 minutes (see Section 5.1.2).
Endogenous insulin sampling			0 (pre-meal), 1, 2, 3, 5, 10, 15, 20, 25, 30, 35, 40, 45, 50, 55, 60, 70, 90, 120, 150, 180, 240, 300, 360 and 420 minutes postmeal	Sampling times are relative to the time of meal administered.
Discharge from CRU			X	Subjects may be discharged after all study procedures are completed. Subjects may be offered a meal following completion of all PK and PD assessments.

Abbreviations: CRU = clinical research unit; ECG = electrocardiogram; MMTT = mixed meal tolerance test; PD = pharmacodynamics; PK = pharmacokinetics.

Note: The CRU should schedule activities as appropriate. In cases where several study procedures are scheduled at the same time, the order of priority will be as follows: PK samples including sampling for blood glucose and laboratory samples per protocol nominal times. ECGs and vital sign measurements should be scheduled before but as close as possible to the PK sampling times.

3. Introduction

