A standardised MMTT will be administered on Day 1 during each of the 4 treatment periods. Patients are expected to complete each standardised test meal within 15 minutes of starting it. Patients will be without further food intake from the start of the meal to completion of blood collection (approximately 420 minutes) unless required to treat hypoglycaemia (see Section 9.4.8).

Following completion of the assessment period and sample collection (approximately 420 minutes), patients will be offered a meal. Patients will continue with the CRU-provided insulin glargine along with their usual bolus prandial insulin. Patients will be observed following administration of the meal and discharged at the investigator's discretion.

After completion of the last treatment period (Period 4), the patients will resume their pre-study basal insulin.

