9.6.2. Glucose Samples (MMTT)

Blood samples will be obtained for the measurement of glucose at the times specified in the Schedule of Activities (Section 2). These glucose measurements will be used for patient safety management as well as for PD evaluations.

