Appendix 5. Blood Sampling Summary

This table summarises the approximate number of venipunctures and blood volumes for all blood sampling (screening, safety laboratories and bioanalytical assays) during the study.

Protocol I8B-MC-ITSL Sampling Summary for Patients

Purpose	Blood Volume per Sample (mL)	Number of Blood Samples	Total Volume (mL)
Screening	11	1	11
Clinical laboratory tests ^a	9	3	27
Dose-finding assessment	0.2	15	3
Blood glucose sampling (run-in)	0.2	13 samples x 4 periods = 52	10.4
Blood glucose sampling (MMTT)	0.2	24 samples x 4 periods = 96	19.2
Pharmacokinetics	3	25 samples x 4 periods = 100	300
Total			370.6
Total for clinical purposes [rounded up to the nearest 10 mL]			380

Abbreviation: MMTT = mixed meal tolerance test.

^a Additional samples may be drawn if needed for safety purposes.

Protocol I8B-MC-ITSL Sampling Summary for Healthy Subjects

Purpose	Blood Volume per Sample (mL)	Number of Blood Samples	Total Volume (mL)
Screening ^a	11	1	11
OGTT	2	3	6
Blood glucose sampling (MMTT)	0.2	24	4.8
Endogenous insulin	3	25	75
Total			96.8
Total for clinical purposes [rounded up to the nearest 10 mL]			100

Abbreviations: MMTT = mixed meal tolerance test; OGTT = oral glucose tolerance test.

^a Additional samples may be drawn if needed for safety purposes.

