### **9.5.6 Blood Glucose Monitoring and Hypoglycemia**

Hypoglycemic events will be appropriately recorded in the CRF. In the case of a hypoglycemic event, the actual blood glucose value, if measured, will be recorded in the CRF, together with any treatments administered. Each category of hypoglycemic events (defined below) will be listed and summarized by treatment during study and during MMTT.

Hypoglycemia is defined as follows:

- **Documented Glucose Alert Level (Level 1)**, Plasma Glucose (PG)  $\leq 70$  mg/dL (3.9 mmol/L):
  - **Symptomatic hypoglycemia**: an event during which typical symptoms of hypoglycemia are accompanied by PG  $\leq 70$  mg/dL (3.9 mmol/L)
  - **Asymptomatic hypoglycemia**: an event not accompanied by typical symptoms of hypoglycemia but with PG  $\leq 70$  mg/dL (3.9 mmol/L)
  - **Unspecified hypoglycemia**: an event during which PG  $\leq 70$  mg/dL (3.9 mmol/L) but no information relative to symptoms of hypoglycemia was recorded
- **Documented Clinically Significant Hypoglycemia (Level 2)** PG  $< 54$  mg/dL (3.0 mmol/L):
  - **Symptomatic hypoglycemia**: an event during which typical symptoms of hypoglycemia are accompanied by PG  $< 54$  mg/dL (3.0 mmol/L)
  - **Asymptomatic hypoglycemia**: an event not accompanied by typical symptoms of hypoglycemia but with PG  $< 54$  mg/dL (3.0 mmol/L)
  - **Unspecified hypoglycemia**: an event during which PG  $< 54$  mg/dL (3.0 mmol/L) but no information relative to symptoms of hypoglycemia was recorded
- **Severe hypoglycemia (Level 3)**: an event requiring assistance of another person to actively administer carbohydrate, glucagon, or other resuscitative actions. During these episodes, the patient has an altered mental status and cannot assist in their care, is semiconscious or unconscious, or experienced coma with or without seizures and may require parenteral therapy. PG measurements may not be available during such an event, but neurological recovery attributable to the restoration of blood glucose concentration to normal is considered sufficient evidence that the event was induced by a low PG concentration (PG  $\leq 70$  mg/dL [3.9 mmol/L])
  - **Severe hypoglycemia requiring medical attention**: a severe hypoglycemic event when patients require therapy by HCPs (EMTs, emergency room personnel, etc)

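### No glucose sample is scheduled after 300 minutes, although patients with T1DM fast and are bled for PK until 420 minutes, so asymptomatic late hypoglycaemia may be missed

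*Protocol*

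**What the plan says.** The glucose schedule for patients with T1DM (Protocol Section 2) closes with "180, 195, 210, 225, 240, 300 minutes post-meal". The insulin PK schedule in the same table closes with "150, 180, 240, 300, 360 and 420 minutes postdose". Appendix 5 confirms both counts: "24 samples x 4 periods = 96" for meal-test glucose and "25 samples x 4 periods = 100" for PK.

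The fast lasts as long as the PK sampling. Section 5.1.1.3 says: "Patients will be without further food intake from the start of the meal to completion of blood collection (approximately 420 minutes"; the only exception is food to treat hypoglycaemia. Glargine continues on meal-test days (Section 3.3). The single bolus is individualised to a test meal of about 100 g carbohydrate (Sections 5.5 and 6.3.1).

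Section 9.6.2 gives the scheduled glucose values two uses: "These glucose measurements will be used for patient safety management as well as for PD evaluations". Hypoglycaemic events are part of the tertiary/exploratory tolerability endpoint (Section 4, Table ITSL.1). SAP 9.5.6 says that each category of event "will be listed and summarized by treatment during study and during MMTT". It gives no time at which the MMTT ends.

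**The concern.** One sampling schedule serves two purposes, and its end fits only one of them. Stopping at 300 minutes matches the longest PD window, ΔAUC(0-5h). The safety use has no such natural end at 5 hours, because the fast and the blood sampling last about two hours longer.

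Asymptomatic Level 1 and Level 2 events exist in the data only if a glucose value was taken. Up to 240 minutes a low would be found by samples every 10 to 15 minutes, whether or not the patient felt it. After 300 minutes it would be found only if something prompted a measurement. A table of events during the MMTT, by treatment, would combine the two modes of detection without showing the change. A patient with an unfelt low in that window could also reach the post-test meal without its having been seen.

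**Working it through.** **1. Reproduce the plan's counts.** Glucose times from Section 2: 3 (−30, −15, 0) + 12 (10 to 120 by 10) + 8 (135 to 240 by 15) + 1 (300) = 24 per period, and 24 × 4 = 96, as in Appendix 5. PK times: 25 per period, and 25 × 4 = 100, also as in Appendix 5. The gap is therefore in the plan and is not a fault of text extraction.

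**2. Samples after 300 minutes.** Glucose: 0. PK: 2, at 360 and 420. Glucose is timed from the meal and PK from the dose. The dose is given immediately before the meal, so I treat the two clocks as one.

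**3. Size of the window.**
- No scheduled glucose: (420 − 300)/420 = 28.6% of the fasting period.
- After the 240-minute sample: (420 − 240)/420 = 42.9% of the period holds one value, at 300.
- Spacing is 10 minutes to 120, 15 minutes to 240, then 60 minutes to 300, then nothing.

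**4. Which events depend on a scheduled value.** Definitions are in Protocol 9.4.6.2 and SAP 9.5.6.
- Severe (Level 3): no glucose value required.
- Symptoms with no value: counted as probable symptomatic.
- Symptomatic Level 1 or 2: needs a value, but symptoms can prompt one. A glucose method giving real-time results is on site during inpatient periods (Section 9.6), and glucose is sampled when treatment is needed (Section 9.4.8).
- Asymptomatic Level 1 or 2: needs a value, and nothing prompts one after 300 minutes.

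Only the last group relies on the schedule.

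**5. Does other monitoring fill the gap?** Section 3.3 promises continuous monitoring during inpatient procedures but names no glucose measurement and no interval. Where the protocol intends glucose checks it states how often: at least every 30 minutes in the run-in (Section 9.6.1) and every 20 minutes in dose-finding (Section 5.1.1.2). Vital signs at 420 minutes and the medical assessment before discharge include no stated glucose value. The dose-finding test also ends at 5 hours, so it gives no scheduled information on this window.

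**6. Cost of two extra readings.**
- Plan's total: 11 + 27 + 3 + 10.4 + 19.2 + 300 = 370.6 mL, which reproduces Appendix 5.
- Added volume: 2 samples × 0.2 mL × 4 periods = 1.6 mL.
- Glucose row: 26 per period, 26 × 4 = 104 samples, 104 × 0.2 = 20.8 mL.
- New total: 370.6 + 1.6 = 372.2 mL, which still rounds up to 380 mL.

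**The case against.** The case for leaving the plan alone has real weight. The 300-minute stop fits every PD endpoint. The hypoglycaemia endpoint is tertiary and descriptive, and SAP 9.5.8 plans no inferential safety analysis. Patients are inpatients with a glucose method at hand, all hypoglycaemic events are recorded, and Section 7.6 lets sampling times be modified on safety information. The dose has been tried beforehand against a 70 to 240 mg/dL range for 5 hours and can be adjusted. All of this stands and limits the importance of the point. None of it produces a glucose value in a patient without symptoms after 300 minutes.

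A reader might infer three stronger things that the documents do not support.

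- *That late hypoglycaemia goes unmeasured.* It has no scheduled measurement. Symptomatic events can be measured or classified, as step 4 of the working shows.
- *That the gap hides the very difference expected between faster-off and slower-off insulins.* Section 3.1 says only that faster-on and/or faster-off characteristics might reduce postprandial hypoglycaemia, and gives no time window. AUC(3-7h) is optional, and its first two hours (180 to 300 minutes) lie inside the glucose schedule.
- *That this is the study's main named risk.* Section 3.3 lists hypoglycaemia first among several risks and does not rank them.

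It is also fair to say that readings at 360 and 420 minutes would be an hour apart, so a short low between them could still be missed. The remedy narrows the gap without closing it.

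**Conclusion.** The point holds in a limited form. For 120 of 420 fasting minutes in each period no glucose value is scheduled, and asymptomatic Level 1 and Level 2 events in that window may be missed. The by-treatment tables for the MMTT would rest on scheduled detection up to 300 minutes and on symptom-driven detection after it.

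The effect is confined to patient safety and the tertiary tolerability endpoint. Early 50% tmax, AUC(0-30min), ΔAUC(0-1h) and ΔAUC(0-5h) are untouched. The documents give no rate of hypoglycaemia after 300 minutes, so neither the number of missed events nor any imbalance between treatments can be estimated.

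The conclusion assumes that continuous monitoring does not already include regular glucose readings in this window. If it does, the protocol needs only to say so, and the missing definition of the MMTT's end remains. The change is worth making because it is cheap, not because the main results are at risk.

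**What to change.** - In the T1DM Schedule of Activities, add a 0.2 mL glucose reading at the existing 360- and 420-minute PK draws in all four periods.
- State that these values are for safety and the hypoglycaemia summaries only, so that ΔAUC(0-5h) is calculated as planned.
- In SAP 9.5.6, define when the MMTT ends for the hypoglycaemia tables, for example at the 420-minute draw or the first food after the test, whichever comes first. SAP 9.4.1 carries glucose values forward to an equally undated end of the MMTT. Say that the new definition applies to the hypoglycaemia summaries and leaves the 5-hour PD calculation alone.
- Update Appendix 5 to 26 samples per period, 104 in total, 20.8 mL; overall 372.2 mL, 380 mL rounded.

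If the sponsor prefers not to add samples, the protocol should state what is measured between 300 and 420 minutes, and the tables should note that detection in that window depends on symptoms.

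The cost is two extra analyser readings per period (2 × 4 = 8 per patient), 1.6 mL more blood per patient and short edits to the protocol and SAP. No visit or venepuncture is added. The change concerns measurement only and sets no dose, feeding or rescue rule.
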